11.3 Secondary Objectives Analysis

The secondary endpoints in terms of HI antibody response against homologous cell-derived vaccine strains (A/H1N1, A/H3N2, B/Yamagata and B/Victoria) at Day 181, are:

- GMT: Geometric mean of HI antibodies at Day 181;
- GMFI: The Geometric mean of the fold increase in serum HI GMTs post-vaccination (Day 181) compared to pre-vaccination (Day 1);
- Percentages of subjects with HI titers \geq 1:40 on Day 181.

In addition, the humoral immune response in terms of MN antibody response against homologous cell-derived vaccine strains (A/H1N1, A/H3N2, B/Yamagata and B/Victoria) at Days 29 and 181:

- GMT: Geometric mean of MN antibodies at Days 29 and 181;
- GMFI: The Geometric mean of the fold increase in serum MN GMTs post-vaccination (Day 29 and Day 181) compared to pre-vaccination (Day 1);
- Percentages of subjects with seroconversion (defined as ≥ 4-fold increase for subjects with prevaccination MN titers ≥ Lower Limit of Quantitation (LLOQ) or as ≥ 4*LLOQ for subjects with pre-vaccination MN titer <LLOQ) at Day 29.

16 MAR 2021 Final Version 2.0

The analysis of the secondary immunogenicity endpoints will be conducted in the same way as described for the primary immunogenicity endpoints.

11.4 Exploratory Objectives Analysis

Post hoc decision will be made to measure titers on Day 1 and Day 29 assessments by the HI assay using *egg*-derived target viruses. These data will be subject to an exploratory analysis along the same methods as for the primary immunogenicity endpoints. Additional analyses may be done on the comparability of the cell and based titers. Details on this exploratory analysis will be included in a separate statistical analysis plan. The results may be presented in an addendum to the CSR.

16 MAR 2021 Final Version 2.0

12. EFFICACY ANALYSIS

Not applicable

16 MAR 2021 Final Version 2.0

13. SAFETY ANALYSIS

The analysis of safety assessments in this study will include summaries of the following categories of safety data collected for each subject:

- Vaccine exposure;
- Solicited local and systemic adverse events;
- Unsolicited adverse events;
- Serious AEs, MAAEs, AESIs and AEs leading to withdrawal from study.

13.1 Analysis of Extent of Exposure

The frequencies of subjects with vaccinations will be summarized overall and by vaccine group and by age group. Data will be tabulated for the All Exposed Set.

13.1.1 Safety Completeness

Analysis Solicited Adverse Events

The safety completeness analysis on solicited adverse events aims to identify subjects who completed the electronic diaries. The analysis will show the number of subjects with results by solicited adverse event and day.

Three summaries will be produced:

- 1. The frequencies of subjects who provided data on the electronic diary cards by vaccine group.
- 2. For each solicited adverse event including analgesic use, the frequencies of subjects with data will be presented by vaccine group and day
- 3. For each solicited adverse event including analgesic use, frequency of the number of days with data on the eDiary by vaccine group.

For the corresponding percentages, the denominator will be the respective number of subjects vaccinated (All Exposed Set).

All analyses will be based on the 'as treated' analysis set.

Document #: FORM2-000092701, Ed: 3.0

13.2 Solicited Local and Systemic Adverse Events

Each solicited AE is to be assessed for Day 1 to Day 7 according to a defined severity grading scale; see specifics of the solicited event and grading system below in Table 3.

 Table 3 Severity Grading for Solicited Local and Systemic Adverse Events

		Any Event			
Туре	Solicited Event	Grade 1/Mild	Grade 2/Moderate	Grade 3/Severe	
Local	Injection site pain	No interference with daily activity	Interferes with daily activity	Prevents daily activity	
	Erythema	25-50 mm	51-100 mm	> 100 mm	
	Induration	25-50 mm	51-100 mm	> 100 mm	
Systemic	Loss of appetite	Eating less than usual with no effect on normal activity	Eating less than usual /interfered with normal activity	Not eating at all	
	Nausea	No interference with daily activity	Interferes with daily activity	Prevents daily activity	
	Fatigue	No interference with daily activity	Interferes with daily activity	Prevents daily activity	
	Myalgia	No interference with daily activity	Interferes with daily activity	Prevents daily activity	
	Arthralgia	No interference with daily activity	Interferes with daily activity	Prevents daily activity	
	Headache	No interference with daily activity	Interferes with daily activity	Prevents daily activity	
	Chills	No interference with daily activity	Interferes with daily activity	Prevents daily activity	
	Fever	38.0 - 38.4 °C 100.4 - 101.1 °F	38.5 – 38.9 °C 101.2 – 102.0 °F	≥39.0 °C ≥102.1 °F	

Note: presence of an event on a day is defined as grade 1, 2 or 3; absence is defined as non-missing and not present. Erythema and Induration: grading will be derived from the actual measurements in mm; Fever will be derived from the actual temperature converted to °C in one decimal.

16 MAR 2021 Final Version 2.0

Other Indicators of Reactogenicity

The use of analgesics/antipyretics will be captured as "absent" or "present" separately by reason "for treatment" or "for prevention".

The analyses will be based on the solicited safety set and encompass various summaries of the data by vaccine group, overall and by age subgroup.

- 1. Overall summary of subjects with solicited adverse events
- 2. Local Solicited adverse events, maximum event severity by event and time interval
- 3. Systemic Solicited adverse events, maximum event severity by event and time interval
- 4. Number of days of solicited adverse events, including ongoing AE after Day 7
- 5. Daily reports of subjects with solicited adverse events.
- 6. Day of first onset of solicited adverse events
- 7. Ongoing adverse events at Day 7
- 8. Distribution of maximum temperature
- 9. Other use of analgesics/antipyretics.

For each of the time points or time intervals presented in the summaries, only subjects with at least one valid observation (i.e., any non-missing values) for the solicited adverse events in the interval of interest will be considered. Subjects without valid data will be removed from the denominator to prevent a downward bias (towards zero).

All tables are run by vaccine group, overall and by age subgroup.

Overall summary of subjects with solicited adverse events.

Any solicited adverse event presence is defined as at least one day recorded a presence of a local or a systemic adverse event. No solicited adverse event is defined as for all days 'No' for all predefined solicited adverse events.

Note that, where applicable, missing values for all days for all events will be excluded from % calculations.

The use of analgesics/antipyretics will be considered in this summary as a separate category under "other", however will be considered as part of reactogenicity.

16 MAR 2021 Final Version 2.0

Local Solicited adverse events, maximum event severity by event and time interval

The **maximum event severity** will be defined if there is at least one non-missing observation within this time interval. Each subject's data will be aggregated across the time points of the interval and summarized according to the maximal severity observed for each local adverse event, followed by a summary across subjects for each vaccine. Subjects with missing values at each of the requested time points, will be excluded.

The time intervals will be Day 1 to Day 7, Day 1 to Day 3 and Day 4 to Day 7. A summary table will be created with the frequency using only any local solicited AE and severe local solicited events.

Systemic adverse events, maximum event severity by event and interval

The analysis on the maximum severity of the systemic adverse events will be done along the same methods as for the local adverse events.

Number of days with solicited adverse events

The number of days with the adverse event is defined irrespective of severity. If a solicited adverse event continues beyond day 7 the period after day 7 is added.

The frequency distribution of the number of days (including mean and median values) will be provided in a summary table by vaccine and by adverse event.

Daily reports of solicited adverse event

For each of the time points only subjects with at least one non-missing observation for the solicited adverse event in the interval of interest will be considered. Subjects with missing values will be removed from the denominator to prevent a downward bias (towards zero). Data collected will be summarized (frequencies and percentages of subjects) by vaccine group, solicited adverse event, and time point (i.e. by day).

Statistical Analysis Plan, Protocol Number V200_10 16 MAR 2021 Final Version 2.0

Time of first onset of solicited adverse events

The **time of first onset** is defined, for each subject, for each solicited adverse event, as the day at which the respective solicited adverse event first occurred. The summary will provide the frequencies and percentages of subjects with first onset of each solicited adverse events by vaccine group and by each time point, as well as mean and median day of onset.

Adverse events ongoing at Day 7

For each of the solicited adverse events, the number and proportion of subjects in the solicited safety set reported the event ongoing at Day 7 will be summarized.

Distribution of maximum temperature

Body temperature will be summarized by 0.5 °C increments from 36.0 °C up to \geq 40 °C by frequency tables.

Use of analgesics/antipyretics

The use of antipyretics and analgesics will be summarized as "other" by type of use (prophylactic versus treatment) as the number and percentage of subjects reporting use.

13.3 Unsolicited Adverse Events

This analysis applies to all AE's occurring during the study, judged either as probably related, possibly related, or not related to vaccination by the investigator, recorded in the AE eCRF, with a start date on (but with onset after vaccination) or after the date of vaccination. AE starting prior to study vaccination will only be listed.

The original verbatim terms used by investigators to identify adverse events in the eCRFs will be mapped to preferred terms using the MedDRA dictionary.

The adverse events will then be grouped by MedDRA preferred terms into frequency tables according to system organ class. All reported AEs, as well as AEs judged by the investigator as at

16 MAR 2021 Final Version 2.0

least possibly related to study vaccine, will be summarized according to system organ class and the preferred term within system organ class. These summaries will be presented by the vaccination group. When an AE occurs more than once for a subject, the maximal severity and strongest relationship to the vaccine group will be counted.

The assignment to safety follow-up time intervals will be done by day of onset and not by days ongoing/persisting.

The summaries will be presented by period of onset (Day 1 to Day 29, Day 30 to end of study or Day 1 to end of study). An overview summary will be created by time -period with number and % of subjects with the following categories:

- AE
- AE by maximum severity
- Related (i.e. at least possible) AE
- SAEs
- Related SAEs
- AESIs
- MAAEs
- AEs leading to withdrawal from study
- Deaths.

The following summaries will be produced by SOC and Preferred Term and by time-period (Day 1 to Day 29, Day 30 to end of study or Day 1 to end of study):

- AEs
- AEs by maximum severity
- AEs that are possibly or probably related to the vaccine
- SAEs
- SAEs that are possibly or probably related to the vaccine

- AESIs
- MAAEs
- AEs leading to withdrawal
- Deaths.

Data listings of all adverse events will be provided by subject. In addition, adverse events in the categories above will be provided as listed data.

All tables will be produced overall and by age subgroup.

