**Figure 3-1: Overview of the Study**

Notes: aDuring this call/visit, non-serious unsolicited adverse events will not be collected. Abbreviations: aQIVc= MF59-adjuvanted Quadrivalent Subunit Inactivated Cell-derived Influenza Vaccine. QIVc= Quadrivalent subunit inactivated cell-derived influenza vaccine. aQIV= MF59-adjuvanted Quadrivalent Subunit Inactivated egg-derived Influenza Vaccine. QIVr= Recombinant Quadrivalent influenza vaccine.

**Duration of the study:** The study duration is approximately 6 months for each subject. The study will be conducted in one single season.

**Vaccination schedule:** Single intramuscular injection on Day 1.

**Investigational Vaccine:** aQIVc.

**Comparator Vaccines:** QIVc, aQIV and QIVr.

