### 7.1.2 Unsolicited Adverse Events

An unsolicited AE is an AE that was not solicited using a Subject eDiary and that was spontaneously communicated by a subject who has signed the informed consent.

Potential unsolicited AEs may be medically attended (defined as symptoms or illnesses requiring hospitalization, or emergency room visit, or visit to/by a health care provider), or were of concern to the subject. In case of such events, subjects will be instructed to contact the site as soon as possible to report the event(s). The detailed information about the reported unsolicited AEs will be collected by the qualified site personnel during the interview and will be documented in the subject’s records.

The period of observation for AEs extends from the time of informed consent until the subject either completes the specified safety follow-up period (Day 181) or at early study termination.

All unsolicited AEs that start during the treatment period (Day 1 to Day 29) will be recorded in the eCRF. During the follow-up (Day 30 to Day 181), unsolicited AEs that meet any reporting criterion (an SAE, AESI, AE leading to withdrawal or a MAAE) are to be recorded in the eCRF.

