### 8.1.2.1 Secondary Safety Endpoints

The secondary safety endpoints include the proportion of subjects reporting solicited and unsolicited adverse events:

- Percentage of subjects reporting a local and/or systemic adverse event for the 7 days following the vaccination (Day 1 to Day 7)
- Percentage of subjects reporting unsolicited adverse events for 28 days following vaccination (Day 1 to Day 29).
- Percentage of subjects reporting serious AEs, MA AEs, AEs leading to withdrawal or AESIs as collected during the study (Day 1 to End of Study).

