##### 8.4.3.1.3 Analysis of Unsolicited Adverse Events

This analysis applies to all AE’s occurring during the study, judged either as probably related, possibly related, or not related to vaccination by the investigator, recorded in the AE eCRF, with a start date on or after the date of vaccination. AE starting prior to study vaccination will only be listed. The original verbatim terms used by investigators to identify adverse events in the eCRFs will be mapped to preferred terms using the MedDRA dictionary.

The adverse events will then be grouped by MedDRA preferred terms into frequency tables according to system organ class. All reported AEs, as well as AEs judged by the investigator as at least possibly related to study vaccine, will be summarized according to system organ class and the preferred term within system organ class. These summaries will be presented by the vaccination group and by the interval of study observation (Day 1 to Day 29, Day 30 to end of study). When an AE occurs more than once for a subject, the maximal severity and strongest relationship to the vaccine group will be counted.

Separate summaries will be produced for the following categories

- AEs
- SAEs
- AEs that are possibly or probably related to the vaccine
- SAEs that are possibly or probably related to the vaccine
- AESIs
- MAAEs
- AEs leading to withdrawal

Data listings of all adverse events will be provided by the subject. In addition, adverse events in the categories above will be provided as listed data.

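### The all-AE, severity and related-AE tables run to the end of study, but after Day 29 only SAEs, AESIs, MAAEs and AEs leading to withdrawal are recorded, so the later and pooled rows are understated and mislabelled

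*SAP*

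**What the plan says.** **Analysis.** SAP section 13.3 asks for an overview table and a set of tables by system organ class and preferred term, overall and by age subgroup. The overview is "presented by period of onset (Day 1 to Day 29, Day 30 to end of study or Day 1 to end of study"). The same three periods apply to the coded tables: "The following summaries will be produced by SOC and Preferred Term and by time-period". The categories include all AEs, AEs by maximum severity and related AEs, the last appearing in the overview as "Related (i.e. at least possible) AE". They stand beside SAEs, related SAEs, AESIs, MAAEs, AEs leading to withdrawal and deaths. Protocol section 8.4.3.1.3 already splits the summaries of all AEs and related AEs "by the interval of study observation (Day 1 to Day 29, Day 30 to end of study"). It lists neither a severity table nor a pooled Day 1-to-end period; both come from the SAP.

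**Collection.** Protocol section 7.1.2 enters all unsolicited AEs in the eCRF if they start on Day 1-29. For Day 30-181 it enters only "unsolicited AEs that meet any reporting criterion (an SAE, AESI, AE leading to withdrawal or a MAAE"). SAP section 3 likewise limits the collection of unsolicited AEs to 28 days.

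**Endpoint.** Protocol section 8.1.2.1 defines the all-AE endpoint for the early period only: "Percentage of subjects reporting unsolicited adverse events for 28 days following vaccination (Day 1 to Day 29"). Its whole-study endpoint is confined to SAEs, MAAEs, AEs leading to withdrawal and AESIs.

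**The concern.** A row called AE for Day 30 to end of study will sit next to a row with the same name for Day 1-29, yet the two do not count the same thing. After Day 29, a subject with a mild complaint for which no care was sought is tabulated as having no AE. The pooled row adds events gathered under both rules and describes neither.

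What is at stake is the descriptive safety record of a vaccine not previously given to humans. Absolute any-AE and related-AE percentages would be too low, the later severity profile would lean towards events that led to medical contact, and part of any fall in AEs after Day 29 would come from the collection rule. The SAP guards against this kind of error for solicited events: section 13.2 removes subjects without valid data from the denominator so that percentages are not pulled towards zero. Section 13.3 has no counterpart.

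**Working it through.** The plan states no figure for this point, so there is none to reproduce. The check sets the table specification against the collection rules.

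**1. What each contact collects**

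- Days 1, 7 and 29: all unsolicited AEs (protocol Table 0-1 and section 5.4.2; SAP Table 1).
- Day 91 call: SAEs, AESIs, MAAEs and AEs leading to withdrawal only (protocol section 5.4.2).
- Day 181 visit: the schedule marks the same four categories and has no entry for unsolicited AEs. The interview in protocol section 5.6 names SAEs, AESIs and MAAEs.
- The note to protocol Figure 3-1 says "During this call/visit, non-serious unsolicited adverse events will not be collected". I do not rely on it. The figure is not available to show which contact is marked, and the wording is wider than section 7.1.2, under which non-serious MAAEs are recorded.

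**2. Share of follow-up under the restricted rule**

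Taking Day 181 as the end of safety follow-up: 181 − 29 = 152 days, and 152/181 = 84%. Full collection covers 29/181 = 16%.

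**3. Direction of the error**

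Let N be the Unsolicited Safety Set, used for all unsolicited AEs (protocol section 8.4.3.1.5). Under SAP section 7.5 it includes subjects whose assessment confirmed no AE. Let A be the number of subjects with any AE starting on Day 30-181, and R the number with at least one reportable AE in that period.

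- Day 30-to-end row: it shows R/N under a label that means A/N. Since R ≤ A, it can only be too low. It is correct only if every subject with a later AE had at least one reportable one. The same holds for related AEs.
- Day 1-to-end row: a subject with an AE by Day 29 is already counted. The shortfall is the number of subjects with no AE by Day 29 and only non-reportable AEs afterwards, divided by N.
- Severity: the events lost are non-serious, not medically attended, not AESIs and not a cause of withdrawal. Most can be expected to be mild, although nothing in the rule prevents a more severe one from being lost.

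**4. Can the shortfall be sized?**

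Not from the documents. As an illustration only, assume a constant AE hazard, a proportion p of subjects with an AE on Day 1-29, and a fraction f of later AEs that are reportable:

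h = −ln(1 − p)/29; full collection = 1 − exp(−152h); shown = 1 − exp(−152hf).

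| p | Full collection, Day 30-181 | Shown, f = 0.3 | f = 0.5 | f = 0.7 |
|---|---|---|---|---|
| 10% | 42.4% | 15.3% | 24.1% | 32.1% |
| 20% | 69.0% | 29.6% | 44.3% | 55.9% |
| 30% | 84.6% | 42.9% | 60.7% | 73.0% |

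The gap runs from 42.4 − 32.1 = 10.3 points to 84.6 − 42.9 = 41.7 points. Neither p, f nor the constant hazard is in the documents. AEs caused by a single vaccination would tend to cluster early, which would lower the full-collection figures. The table shows that the size depends on the inputs; it is not an estimate.

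**The case against.** The strongest reply is that nothing is miscounted. SAP section 13.3 limits the analysis to events "recorded in the AE eCRF", SAP section 3 states the collection rule, and the period boundary falls exactly where the rule changes. A careful reader can therefore take the Day 30-to-end row as reportable AEs. This stands in part: the fault is a row whose name does not match its content, not a programming error. It does not rescue the pooled row, where the two rules can no longer be separated.

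A reader might also infer that the tables give false reassurance against the 180-day safety objective. The documents do not support that. Every pre-specified whole-study safety endpoint is a category collected throughout and has its own row, and the all-AE endpoint stops at Day 29, where collection is complete.

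Nor do they support an inference of bias towards one vaccine. The rule is the same in all four arms of an observer-blind study, and the safety analysis is descriptive.

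The general statement in protocol sections 7.1 and 7.1.2 that AEs are observed to Day 181 does not remove the point, because section 7.1.2 goes on to restrict what is recorded after Day 29.

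Finally, SAP section 17 leaves the tables to separate shells, which are not available here. A footnote may exist there. What can be said is that neither the SAP nor the protocol calls for one.

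**Conclusion.** The point holds as a mismatch between table specification and data collection. The affected rows are any AE, AE by maximum severity and related AE for Day 30 to end and Day 1 to end of study in SAP section 13.3, and all and related AEs for Day 30 to end in protocol section 8.4.3.1.3. Their percentages cannot be too high and will be too low unless every subject with a later AE also had a reportable one. That direction rests only on the collection rule and the denominator. The expected loss of mainly mild events is an inference from the reporting criteria.

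The firm figure is 152 of 181 days under restricted collection. No size for the shortfall should be quoted, since it would rest on assumptions from outside the documents.

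**What to change.** In SAP section 13.3 and protocol section 8.4.3.1.3:

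- Restrict the all-AE, AE-by-maximum-severity and related-AE tables to onset on Day 1-29, and drop the pooled Day 1-to-end versions.
- For Day 30 to end and Day 1 to end, tabulate events that are an SAE, AESI, MAAE or AE leading to withdrawal under the name reportable AEs, with severity and relatedness. In the Day 1-to-end table, apply the same four criteria to events from Day 1-29, so that one rule covers the whole period.
- Keep the existing individual category rows and deaths for all periods.

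The combined reportable-AE row is needed because, if severity and relatedness were shown only within MAAEs, they would be lost for a non-serious AESI or withdrawal AE that was not medically attended.

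The cost is wording in two sections and changes to table shells; data collection does not change. The downside is that there would be no all-AE figure for the whole study, which the collected data cannot supply in any case.
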